Patients who discontinued from treatment for reasons other than PD will continue disease assessments until confirmed PD or start of subsequent anticancer therapy.

The response to immunotherapy may differ from the typical responses observed with cytotoxic chemotherapy including the following:

- Response to immunotherapy may be delayed,
- Response to immunotherapy may occur after PD by conventional criteria,
- The appearance of new lesions may not represent PD with immunotherapy, and/or
- SD while on immunotherapy may be durable and represent clinical benefit.

Based on the above-described unique response to immunotherapy and based on guidelines from regulatory agencies, e.g., European Medicines Agency's "Guideline on the evaluation of anticancer medicinal products in man" (EMA/CHMP/205/95/Rev.4) for immune modulating anticancer compounds, this study will include the following in addition to standard RECIST 1.1 criteria:

- RECIST will be modified so that PD must be confirmed with a second radiologic assessment, preferably, 5 weeks (+/- 7 days) after the initial assessment of PD in the absence of clinically significant deterioration. Treatment with study regimen should continue between the initial assessment of progression and confirmation for progression at outlined in Tables 4.
- In addition, subjects may continue to receive the study regimen beyond confirmed PD in the absence of clinically significant deterioration and if investigators consider that subjects may be deriving benefit from treatment and there are no more suitable alternative treatments available for the subject.

Version Number: 1.8

Proprietary of MD Anderson Cancer Center Date: July 26, 2019

Modification of RECIST as described is meant to discourage the early discontinuation of the study regimen and provide a more complete evaluation of its anti-tumor activity than would be seen with conventional response criteria. Nonetheless, the efficacy analysis will be conducted by programmatically deriving each efficacy endpoint based on the first evidence of progression (by modified RECIST 1.1 criteria described below) when progression is confirmed by a second scan.

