8.2.1. Efficacy analysis set

Response-evaluable Population: The co-primary endpoint of ORR by RECIST v1.1 will be based on the Response-evaluable Population. This population will include all patients with confirmed HPV-16 or HPV-18 associated disease who have received any dose of both study drugs, have a baseline scan with measurable disease, and have at least one follow-up scan (includes discontinuations due to disease progression or death without follow-up scan) with \geq 16 weeks follow-up.

Secondary efficacy analyses will be based on both the Response-evaluable and the As-treated populations. The As-treated Population will include all patients who receive any IP (defined as at least one dose of either study drug).

Table 6 provides a summary of the efficacy endpoints with their corresponding methods of assessment and populations.

Table 6. A Summary of Efficacy Endpoints with Corresponding Methods of Assessment and Populations

unu i opunutons			
Type of efficacy endpoint	Endpoint	Method	Population(s)
Primary	ORR	RECIST version 1.1	Response-evaluable
Secondary	ORR	RECIST version 1.1	As-treated
	ORR	irRECIST	Response-evaluable and As-treated
	DCR-24w	RECIST version 1.1	Response-evaluable and As-treated
	PFS	RECIST version 1.1	Response-evaluable and As-treated
	OS	Kaplan-Meier	Response-evaluable and As-treated

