8.3. Outcome Measures

8.3.1. Primary

The primary objective will be measured by ORR by RECIST v1.1. The ORR will be estimated along with corresponding 95% confidence interval. All analysis will be done within each cohort as well as across all cohorts.

All RECIST assessments, whether scheduled or unscheduled, will be included in the calculations. This is also regardless of whether a patient discontinues study treatment or receives another anticancer therapy.

At each visit, patients will be assigned a RECIST version 1.1 visit response of CR, PR, SD, or PD depending on the status of their disease compared with baseline and previous assessments by the investigator. Baseline will be assessed within the 28 days prior to enrollment. If a patient has had a tumor assessment that cannot be evaluated, then the patient will be assigned a visit response of not evaluable (unless there is evidence of progression in which case the response will be assigned as PD).

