8.3.2. Secondary

The secondary objectives will be measured by the following:

- AEs/SAEs;
- Collection of hematology, serum chemistry, urinalysis, creatine phosphokinase, thyroid function testing and pregnancy test;
- Electrocardiograms. The following parameters will be recorded for each electrocardiogram: date and time of electrocardiogram, heart rate (beats/min), PR, QRS, RR interval, QT (ms), QTcF (ms), sinus rhythm (yes/no), and overall evaluation (normal/abnormal);
- Vital signs;
- Physical examinations;
- Concomitant medications;
- OS;
- PFS as assessed by RECIST v1.1;
- ORR by RECIST v1.1;
- Immune-related RECIST; and
- Disease control rate at 24 weeks by RECIST v1.1.

Safety will be summarized by the percentage of patients with AEs, with grading(according to CTCAE v4.03) and attribution. Summary statistics will also be provided for serious AEs, hematology, urinalysis, CPK, thyroid function testing, pregnancy test, ECG, vital sign, physical examinations and concomitant medications.

Version Number: 1.8 Date: Inly 26, 2019 Proprietary of MD Anderson Cancer Center

8.3.2.1. **Objective Response Rate (ORR)**

Objective response rate will be assessed as a secondary endpoint in the As-treated Population using RECIST version 1.1. Objective response rate will be also assessed in the Response-evaluable and As-treated populations using irRECIST.

8.3.2.2. **Progression Free Survival (PFS)**

Progression free survival measures progression by growth of the primary tumor, nodal spread metastases, death from the cancer, or death from other causes. Progression free survival will be assessed by the periodic tumor assessment using imaging per the institutional guidelines at the schedules according to Table 3.

All study evaluations for disease response must be based on RECIST v1.1.

Progression free survival will be defined as the time from the date of start of IP treatment until the date of objective disease progression or death (+1 day) (by any cause) whichever occurs first. Patients who have not progressed or died at the time of the analysis will be censored at the time of the latest date of assessment from their last evaluable RECIST version 1.1 assessment. However, if the patient progresses or dies after two or more missed visits, the patient will be censored at the time of the latest evaluable RECIST version 1.1 assessment prior to two missed visits.

The PFS time will always be derived based on scan/assessment/death dates and not visit dates.

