RECIST version 1.1 assessment/scans contributing towards a particular visit may be performed on different dates. The following rule will be applied:

For investigator assessments, the date of progression will be determined based on the earliest of the RECIST version 1.1 assessment/scan dates of the component that indicates progression.

When censoring a patient for PFS, the patient will be censored at the latest of the dates contributing to a particular overall visit assessment.

Note: For target lesions, only the latest scan date is recorded out of all scans performed at that assessment for the target lesions, and similarly for non-target lesions, only the latest scan date is recorded out of all scans performed at that assessment for the non-target lesions.

PFS will be assessed in the Response-evaluable and As-treated populations.

8.3.2.3. **Disease Control Rate (DCR)**

Disease control rate is defined as N (%) patients with CR, PR, or SD by 24 weeks on study using RECIST version 1.1. For SD determination for DCR, the patient must have lack of progression for the first 24 weeks on study. Disease control rate will be assessed in the Response-evaluable and As-treated populations.

8.3.2.4. **Overall Survival (OS)**

OS is defined as the time from the date of start of IP treatment until death (+1 day) due to any cause. Any patient not known to have died at the time of analysis will be censored based on the

Version Number: 1.8 Date: July 26, 2019

Proprietary of MD Anderson Cancer Center

last recorded date on which the patient was known to be alive. OS will be assessed in the Response-evaluable and As-treated populations.

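### Section 6.3 counts a progression only once a second scan confirms it, but Section 8 has no such condition, so PFS and DCR-24w depend on which section is programmed

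*Combined protocol and SAP*

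**What the plan says.** **Section 6.3 (Efficacy Assessments).** RECIST is modified so that PD needs a second radiologic assessment unless there is clinically significant deterioration. Efficacy endpoints are then derived by program "based on the first evidence of progression (by modified RECIST 1.1 criteria described below) when progression is confirmed by a second scan". That sentence does not repeat the deterioration exception. The criteria it announces do not follow; only a definition of deterioration does.

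**Section 8 (Statistical Analyses).**
- Section 8.3.1: "At each visit, patients will be assigned a RECIST version 1.1 visit response of CR, PR, SD, or PD". All assessments enter the calculations: "This is also regardless of whether a patient discontinues study treatment or receives another anticancer therapy".
- Section 8.3.2.2: PFS runs "until the date of objective disease progression or death (+1 day) (by any cause) whichever occurs first", and progression is dated by the earliest component scan showing it. A patient with no event is censored at the last evaluable assessment. "However, if the patient progresses or dies after two or more missed visits, the patient will be censored" at the last evaluable assessment before the gap.
- Section 8.3.2.3: "For SD determination for DCR, the patient must have lack of progression for the first 24 weeks on study".
- Section 8.2.1: Table 6 names plain RECIST version 1.1 for ORR, DCR-24w and PFS, and irRECIST only for a second ORR.

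In Section 8 the word confirmed is applied to HPV status, never to PD.

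**Continued scanning.** Section 6.3 says: "Patients who discontinued from treatment for reasons other than PD will continue disease assessments until confirmed PD or start of subsequent anticancer therapy". It also plans a single assessment at end of treatment when PD is seen there, and Table 3 (footnote k) schedules post-treatment scans only for patients without PD.

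**The concern.** Two programmers working from the same document could produce different PFS and DCR-24w results. The literal Section 6.3 route is also biased in one direction. A patient who shows growth and then has no further evaluable scan leaves the risk set without an event, at the moment when failure has just been observed. Kaplan-Meier assumes that censored patients have the same outlook as those still followed, and these patients plainly do not.

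PFS and DCR-24w carry no numeric threshold. However, the trial has no control arm to absorb a shared bias, and Section 1.3.2 lists both among the endpoints that will inform whether further studies are warranted.

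**Working it through.** **Step 1: the plan's own design figure, as a baseline.** Section 8.1 gives a Simon two-stage design: stop at 1 or fewer responses in 9, succeed at 9 or more in 34, ORR 0.15 against 0.35. Exact binomial calculation gives one-sided alpha 0.0474, power 0.811 and a probability of early stopping under the null of 0.599. The maximum is 9 + 2 × 34 = 77. The design reproduces and is not in question.

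**Step 2: the two sections side by side.**

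| First PD, then | Section 8 alone | Literal Section 6.3 with 8.3.2.2 censoring |
|---|---|---|
| second scan confirms | event at first PD | event at first PD |
| (a) second scan does not confirm | event at first PD | no event; follow-up continues |
| (b) no later evaluable scan, patient alive | event at first PD | censored at last evaluable assessment, which is the PD scan |
| (b) no later evaluable scan, patient dies | event at first PD | event at death, unless two or more visits were missed first |

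The censoring entry is an inference: a PD that is not an event leaves the patient in the group that has not progressed. Routes into (b) are new anticancer therapy (when planned scans end), dropout, a missed or unevaluable scan, and PD at end of treatment if only the single planned assessment is done.

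**Step 3: size per patient in case (b).** The documents give no PFS assumption, so the cohort is illustrative: n = 34, scans at weeks 8, 16 and 24, first PDs 12, 8 and 5, no other losses. Section 6.3 sets 8-weekly scans; Table 3 marks weeks 12 and 20.

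With every first PD an event: (22/34) × (14/22) × (9/14) = 9/34 = 26.5%.

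Censoring one PD at its own scan raises the estimate by (1/34) × (proportion of patients past that scan who remain progression-free at week 24):
- week 8: (1/34) × (9/22) = 1.2 points, giving 27.7%
- week 16: (1/34) × (9/14) = 1.9 points, giving 28.4%
- week 24: 1/34 = 2.9 points, giving 29.4%

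Three such patients at one scan give 30.1% (week 8) to 35.3% (week 24).

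**Step 4: size per patient in case (a).** A week 8 PD that is not confirmed, in a patient still progression-free at week 24, gives (23/34) × (15/23) × (10/15) = 10/34 = 29.4%, or 2.9 points above Section 8. If that patient has a confirmed PD at week 16 instead, 24-week PFS stays at (23/34) × (14/23) × (9/14) = 9/34 and only the event date moves.

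**Step 5: size by assumed frequency, case (b).** Let u be the share of first PDs with no second scan. With exponential progression, 8-weekly scans and no deaths, 24-week PFS = (1 − (1 − u)h)³, where h = 1 − 2^(−8/median).

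| Median (weeks) | u = 0 | 5% | 10% | 20% |
|---|---|---|---|---|
| 10 | 0.189 | 0.211 | 0.235 | 0.287 |
| 13 | 0.278 | 0.301 | 0.325 | 0.377 |
| 17 | 0.376 | 0.398 | 0.421 | 0.470 |

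The shifts are about 2, 4.5 to 4.7, and 9.4 to 9.9 points. They are upper values for these assumptions, because later deaths that count as events reduce them.

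**Step 6: sampling error.** The exact 95% interval for 9/34 is 12.9% to 44.4%.

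**The case against.** The strongest reply is that Section 6.3 is the specific text on how endpoints are derived, and that Section 8's silence does not revoke it. Treatment and scanning normally continue to confirmed PD, so most first PDs will be rescanned. Deterioration, including rapid progression that forces other therapy, is exempt from confirmation under the Section 6.3 bullet.

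Much of this stands. If the exemption is read into the derivation sentence, deterioration is largely covered. Slower progression followed by new therapy, dropout or an unevaluable scan is not. Making Section 6.3 govern does not cure case (b) either, because it is the Section 6.3 reading that produces the informative censoring.

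Four inferences go further than the documents allow:
- **That no rule reaches these patients.** Each section yields an answer; the answers differ.
- **That the difference vanishes if every first PD is rescanned.** It does not, because case (a) remains.
- **That the ORR boundaries (2/9, 9/34) are at risk from missing second scans.** A later response needs a later scan, so a case (b) patient cannot supply one. Response after a first PD is a separate question, partly addressed by the irRECIST ORR.
- **That DCR-24w is heavily inflated.** Section 8.3.2.3 does not say whether an unconfirmed PD breaks disease control, but a patient whose last assessment is PD is not naturally counted as controlled. On that reading there is no shift from case (b).

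**Conclusion.** The inconsistency is real and minor. Sections 6.3 and 8 give different PFS results for a first PD that a later scan does not confirm and for a first PD with no later evaluable scan. In the second situation, literal Section 6.3 with the Section 8.3.2.2 censoring rule biases PFS upward.

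In the illustrative cohort, each case (b) patient adds about 1.2 to 2.9 points to 24-week PFS. That is well inside one cohort's sampling error, but the shift always runs in the favourable direction. One patient reclassified on DCR-24w would move it by 1/34 = 2.9 points.

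The frequency of such patients, the PD times and the median time to progression are all assumptions. The conclusion about direction in case (b) does not depend on them; the size does.

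**What to change.** The change is to the analysis only. Use one PD definition in Sections 6.3, 8.3.1, 8.3.2.2 and 8.3.2.3 and in Table 6. If confirmation is kept, state that:
- a first PD disproved by a later evaluable scan, taken before any new anticancer therapy, is not an event;
- any other first PD, including one followed by deterioration, new therapy or no further scan, is a PFS event at its own scan date and is not disease control at 24 weeks.

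The restriction to scans before new therapy needs stating because Section 8.3.1 admits later scans to its calculations. Report PFS and DCR-24w by unconfirmed RECIST 1.1 as a sensitivity analysis, with counts of first PDs that were confirmed, disproved, or without a second scan.

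Separately, say whether a response on a later scan after a first PD counts in the RECIST 1.1 ORR or only in the irRECIST ORR. Sections 3.4 and 6.3 also word the timing of the confirming scan differently (next assessment but at least 4 weeks later; preferably 5 weeks). The sponsor must reconcile them; no timing is proposed here.

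The cost is about a paragraph of text and no new data. Reported PFS will be slightly less favourable than under literal Section 6.3, and a true pseudoprogression with no later scan will count as an event. The three counts make that visible.

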6.5.1. Laboratory safety assessments

Clinical laboratory tests (blood and urine) will be performed as detailed in the Schedule of Study Procedures (Table 3).

6.5.2. Serology

Antibodies to HBV and HCV will be measured. Antibodies to HIV will only be measured if clinically indicated.

Patients with a positive HBV surface antigen (HBsAg) test at screening are not eligible for the study.

Patients who are HBsAg and HBV core antibody (HBcAb) negative but are positive for HBsAb may be included in the study provided that all other eligibility criteria are satisfied.

A HBV DNA test will be performed if the patient is HBsAg negative but HBcAb positive (regardless of HBsAb status).

If the HBV DNA test is positive, the patient will be excluded.

If the HBV virus DNA test is negative, the patient may be included in the study.

Prophylactic antiviral therapy, in addition to the monitoring described above, may be initiated at the discretion of the investigator.

If the patient becomes hepatitis virus DNA positive during the study, the investigator will manage the clinical situation as per the standard of care of that institution and the medical monitor will be notified.

Version Number: 1.8 Date: July 26, 2019

Proprietary of MD Anderson Cancer Center

6.5.3. Pregnancy testing

For women of childbearing potential, a negative result for serum pregnancy test (β -HCG) must be available at the screening visit, prior to the collection of the tumor biopsy, and prior to each administration of IP. If at any point, the pregnancy test is positive, indicating that the patient is pregnant, no additional IP will be administered, but the patient will be followed for the duration of the study and beyond to determine the outcome of the pregnancy (with the patient's consent).

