4.4. Doses and Treatments

4.4.1. Planned Dosing Schedule

All patients will receive combination treatment with MEDI0457 and durvalumab as per the following **Planned Dosing Schedule** (treatment should be given at the beginning of the week, unless otherwise specified) as detailed in **Figure 1** and **Table 3**.

Durvalumab will be administered at a fixed dose of 1500 mg q4wk for patients that are \ge 30 kg. For patients who weigh <30 kg, weight-based dosing will be used at a dose of 20 mg/kg q 4 weeks, and if their weight increases to \ge 30 kg they can be switched to durvalumab at 1500 mg every 4 weeks.

Patients will receive 7 mg MEDI0457 delivered by IM followed by EP on Day 1 (Week 1), Week 3, Week 7, Week 12 and then every 8 weeks until disease progression or unacceptable toxicity. Durvalumab will be administered on Week 4, Week 8, Week 12 and then every 4 weeks until disease progression or unacceptable toxicity. On days when both MEDI0457 and durvalumab administrations will occur on the same day (Week 12 then every 8 weeks), MEDI0457 will be administered first, and durvalumab IV infusion will start approximately 1 hour after MEDI0457 is delivered intramuscularly followed by EP.

Minimum time between Week 3 MEDI0457 dose and the Week 4 first durvalumab dose, and the Week 7 MEDI0457 dose and the Week 8 durvalumab dose is 7 days.

Version Number: 1.8 Proprietary of MD Anderson Cancer Center Page 1019 26 2019

4.4.2. **Durvalumab**

Durvalumab will be administered at a fixed dose of 1500 mg q4w in the combination and monotherapy arms for patients weighing \geq 30 kg. For patients weighing \leq 30 kg, the dose will be 20 mg/kg. The maximum number of doses of checkpoint inhibitor therapy will equal 13.

The duration will be approximately 1 hour (± 5 minutes) for each durvalumab infusion. A 1- hour observation period is required after the first infusion of durvalumab is administered. If no clinically significant infusion reactions are observed during or after the first dose, subsequent infusion observation periods can be at the investigator's discretion (suggested 30 minutes after each durvalumab infusion).

Patients will be monitored during and after the infusion with assessment of vital signs at the times specified in the study protocol.

See Section 6.7.1 dose administration changes in the event of Grade 1 or 2 infusion-related reactions.

4.4.3. **MEDI0457**

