5. STUDY PLAN

All study procedures will be performed according to **Table 3**.

Version Number: 1.8 Date: July 26, 2019

Proprietary of MD Anderson Cancer Center

Table 3. Schedule of Study Procedures

	Screening	(Cycle 1		Cyc	ele 2	Cy	cle 3	Cycle 4 ^a	Cycle 5 ^a	EOT ^b	Follow-up ^c
Week of Study	-	1	3	4	7	8	10	12	16	20	-	-
Procedures Day of Week	-28 to -1	1 ±7 days (unless otherwise noted)										
Informed consent	X											
Demographics	X											
Medical histories ^d	X											
Inclusion/exclusion criteria	X	X										
Physical examination ^e	X	Xf	X	X	X	X	X	X	X	X	X	
ECOG performance status	X	X^{f}	X	X	X	X	X	X	X	X	X	
Adverse events assessment	X	X	X	X	X	X	X	X	X	X	X	
Concomitant medications/procedures	X	X	X	X	X	X	X	X	X	X	X	
Disease status ^g	X ^h							Xi		X ^{i,j}	X	X^k
Hepatitis/HIV screening ¹	X											
Vital signs ^m	Xg	Xf	X	X	X	X	X	X	X	X	X	
12-lead ECG	X	Xf				X		X		X ⁿ	X	
HPV typing ^o	X											
Hematology ^p	X	Xf	X	X	X	X	X	X	X	X^q	X	
Serum chemistry ^r	X	Xf	X	X	X	X	X	X	X	X^q	X	
Coagulation testing ^s	X	As clinically indicated.										
Thyroid function testing ^t	X	X^{f}		X		X		X	X	X^q	X	
Urinalysis ^u	X	As clinically indicated.										
Pregnancy test ^v	X^{w}	X ^x		X		X		X	X	X	X	
MEDI0457 administration ^y		X	X		X			X		X		
MEDI0457 post-treatment reaction ^z		X	X		X			X		X		
Download EP data		X	X		X			X		X		
Durvalumab administration ^{aa}				X		X		X	X	X		
Tumor biopsy ^{bb}	X						Xcc				X^{dd}	
Immune Profiling/HPV Serology Research Bloodee		X		X		X	X		$X^{\rm ff}$		X	
Pharmacokinetics/ADA Research Blood ^{gg}				X		X			X^{hh}			
Viral load ⁱⁱ	X			X		X		X	X	X	X	
HBV DNA/Hep BsAg ^{jj}				X		X		X			X	

Version Number: 1.8

Proprietary of MD Anderson Cancer Center Date: July 26, 2019

- ^a Patients can continue on the study until progression or unacceptable toxicity as long as the physician feels the patient is receiving benefit. Cycles 4 and 5 should be repeated to continue this treatment. ^b End of treatment (EOT) is defined as the last visit where the decision is made to discontinue protocol directed treatment.
- ^c A clinic visit is not required for follow-up. Patients who are taken off study due to disease progression or intolerable toxicities will be followed for vital status every 6 months via phone and/or review of medical record.
- ^d Histories include medical history, history of prior cancer treatment, history of procedures

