- Serum Chemistry panel includes: albumin, alkaline phosphatase, ALT, AST, bicarbonate, calcium, chloride, glucose, lactate dehydrogenase, magnesium, potassium, sodium, total bilirubin (if Total bilirubin is $\ge 2x$ ULN [and no evidence of Gilbert's syndrome] then fractionate into direct and indirect bilirubin), total protein, creatinine, creatinine phosphokinase, blood urea nitrogen, uric acid, amylase and lipase. Please note: GGT to be collected at baseline and as clinically indicated.
- ^s Prothrombin time, APTT and INR.
- Free triiodothyronine (T₃) and free thyroxine (T₄) will only be measured if TSH is abnormal. They should also be measured if there is clinical suspicion of an AE related to the endocrine system.
- ^u Urinalysis panel includes: bilirubin, blood, glucose, ketones, pH, protein, specific gravity, and color/appearance.
- ^v Only for women of childbearing potential.
- To include luteinizing hormone and follicle-stimulating hormone only for women of child bearing potential who may be post-menopausal.
- x Patients with a negative serum pregnancy test within 3 days prior to Day 1 do not require a Week 1 Day 1 pregnancy test to be performed.
- y A window of ±3 days for all time points except C1D1. For Cycles 1 and 2, an interval of 7 days must occur between MEDI0457 and durvalumab treatments.
- ² MEDI0457 post-treatment reactions will be assessed 30 to 60 min after study treatment.
- ^{aa} A window of ± 3 days applies to all time points.
- bb Core tumor biopsies will be collected as per **Section 6.6.1**.
- cc ± 3 days. Biopsies at this time point are required until 10 subjects have provided tissue and then are optional for all subsequent subjects.
- dd At time of confirmed disease progression; Optional
- ^{ee} See **Section 6.6.2.1** for HPV Serology Research Blood details.
- ff Week 16 and then every 8 weeks until end of treatment.
- gg See Section 6.6.2.2 for Pharmacokinetics/ADA details.
- hh Week 16 only.
- ii For HIV(+) patients, viral load will be drawn at baseline, every month for the first 3 months, then every 3 months thereafter while on therapy.
- ^{jj} For patients with inactive Hepatitis B (Hep B core Ab(+)/HepB sAg (-)), HBV DNA and Hep BsAg will be monitored every month for the first 3 months, then every 3 months thereafter while on therapy.

Version Number: 1.8 Date: July 26, 2019 Proprietary of MD Anderson Cancer Center

STUDY ASSESSMENTS 6.

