7.6.2. Maternal exposure

If a patient becomes pregnant during the course of the study, the IPs should be discontinued immediately.

Pregnancy itself is not regarded as an AE unless there is a suspicion that the IP under study may have interfered with the effectiveness of a contraceptive medication. Congenital abnormalities or birth defects and spontaneous miscarriages should be reported and handled as SAEs. Elective

Version Number: 1.8 Date: July 26, 2019

Proprietary of MD Anderson Cancer Center

abortions without complications should not be handled as AEs. The outcome of all pregnancies (spontaneous miscarriage, elective termination, ectopic pregnancy, normal birth, or congenital abnormality) should be followed up and documented even if the patient was discontinued from the study.

If any pregnancy occurs in the course of the study, then the Investigator or other site personnel should inform the appropriate AstraZeneca representatives within 1 day, i.e., immediately, but **no later than 24 hours** of when he or she becomes aware of it.

The designated AstraZeneca representative will work with the Investigator to ensure that all relevant information is provided to the AstraZeneca Patient Safety data entry site within 1 to 5 calendar days for SAEs and within 30 days for all other pregnancies.

The same timelines apply when outcome information is available.

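### Section 6.5.3 requires a negative serum pregnancy test before every IP dose, but Table 3 schedules none at the Week 3 and Week 7 MEDI0457 doses

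*Combined protocol and SAP*

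**What the plan says.** Section 6.5.3 applies to women of childbearing potential. It requires a negative serum beta-HCG result that "must be available at the screening visit, prior to the collection of the tumor biopsy, and prior to each administration of IP". A positive result at any point stops further IP.

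MEDI0457 is one of the investigational products listed in Section 4.1. Section 4.4.1 has "MEDI0457 delivered by IM followed by EP on Day 1 (Week 1), Week 3, Week 7, Week 12 and then every 8 weeks". Durvalumab is given at Weeks 4, 8 and 12 and then every 4 weeks.

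Section 5 introduces Table 3 with "All study procedures will be performed according to" that table. Section 6.5.1 adds that the clinical laboratory tests on blood and urine "will be performed as detailed in the Schedule of Study Procedures", which is again Table 3. Three footnotes attach to the pregnancy-test row:

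- Footnote v limits it to women of childbearing potential.
- Footnote w adds hormone levels at screening for women who may be post-menopausal.
- Footnote x says patients with a "negative serum pregnancy test within 3 days prior to Day 1 do not require a Week 1 Day 1 pregnancy test".

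Section 7.6.2 states the consequence of a pregnancy: "If a patient becomes pregnant during the course of the study, the IPs should be discontinued immediately".

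**The concern.** The text rule covers every dose of either product. The schedule's pregnancy-test marks after Week 1 fall only on durvalumab visits and at end of treatment, so two vaccine-only visits are left out. A coordinator working from Table 3 would not order the test at Weeks 3 and 7. A monitor working from Section 6.5.3 could record a deviation for each of those doses. I found no rule saying which of the two takes precedence.

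The test is what triggers the stop to dosing. Without it, a woman who became pregnant after the Week 1 or Week 4 test could receive another vaccine dose before anyone knew. Women are central to this trial: one cohort is cervical cancer, another includes vulvar and vaginal cancer, and the first three patients must have one of these three cancers.

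**Working it through.** **Inputs.** Table 3 has 12 columns: Screening; Weeks 1, 3, 4, 7, 8, 10, 12, 16 and 20; end of treatment; follow-up. The pregnancy-test, MEDI0457 and durvalumab rows each split into 12 cells. The two dosing rows give the weeks stated independently in Section 4.4.1, so the column alignment is sound and the blanks are not an artefact of text extraction.

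| Week | IP given | Pregnancy test in Table 3 |
|---|---|---|
| 1 | MEDI0457 | yes |
| 3 | MEDI0457 | **no** |
| 4 | durvalumab | yes |
| 7 | MEDI0457 | **no** |
| 8 | durvalumab | yes |
| 12 | both | yes |
| 16 | durvalumab | yes |
| 20 | both | yes |

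**Coverage through Week 20.**

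- Dosing visits without a test: 2 of 8 (25% of scheduled visits, not of patients).
- MEDI0457 doses without a test: 2 of 5.
- Durvalumab doses without a test: 0 of 5.
- Vaccine-only visits (Weeks 1, 3, 7) without a test: 2 of 3.

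Cycles 4 and 5 repeat thereafter (footnote a) and carry a test at each dosing visit, so the gap does not recur. Section 4.4.2 caps durvalumab at 13 doses, nominally Weeks 4 to 52 (4 + 12 × 4 = 52). The later vaccine doses (Weeks 12, 20, 28, 36, 44, 52) all fall on durvalumab visits. A patient completing that course has 3 + 13 = 16 dosing visits, and 2/16 = 12.5% lack a test.

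**Age of the last scheduled result at the untested doses.** Count Week 1 as Day 1, Week 3 as Day 15, Week 4 as Day 22, Week 7 as Day 43 and Week 8 as Day 50. For vaccine doses, footnote y gives "A window of ±3 days for all time points except C1D1".

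- Week 3, nominal: 15 − 1 = 14 days. Minimum: 14 − 3 = 11 (dose 3 days early). Maximum: 14 + 3 + 3 = 20 (dose 3 days late, and the Day 1 test replaced under footnote x by one 3 days earlier).
- Week 7, nominal: 43 − 22 = 21 days. With the table's default ±7 days for the Week 4 test and ±3 days for the dose: 21 − 10 = 11 to 21 + 10 = 31. If the test is drawn at the durvalumab visit (±3 days): 21 − 6 = 15 to 21 + 6 = 27.

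**Next scheduled test after each untested dose.** Day 22 − Day 15 = 7 days, and Day 50 − Day 43 = 7 days, both nominal. Under the default ±7-day window a Week 4 or Week 8 test could fall up to 3 days before the Week 3 or Week 7 dose, but nothing in the schedule asks for that.

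**After the fix.** Marks at Weeks 3 and 7 raise coverage through Week 20 from 6/8 to 8/8.

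**The case against.** Four points can be made for leaving the plan alone.

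1. Section 6.5.3 is mandatory and nothing cancels it, so a site that follows the whole protocol tests at Weeks 3 and 7. This is fair: the plan does not direct untested dosing. But Sections 5 and 6.5.1 send sites to Table 3, and a schedule that leaves out a required safety test invites the omission.

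2. The rule asks that a result be *available* and sets no age limit, so the Week 1 or Week 4 result might serve. Read that way, one screening result would cover every dose and the reference to each administration would do no work. Footnote x accepts an earlier result for Day 1 only within 3 days. It governs Day 1 alone, but it shows that recency mattered to the authors.

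3. The marks fit a deliberate 4-weekly plan, in which case Section 6.5.3 is the loose text. The documents do not settle the intent, and this point stands. It changes which text to correct, not whether a correction is needed.

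4. The 25% figure depends on stopping at Week 20; over a full durvalumab course it is 12.5%. That is also true. The substance is two early visits, whichever denominator is used.

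**Conclusion.** The inconsistency is real: Section 6.5.3 and Table 3 cannot both be followed as written at the Week 3 and Week 7 MEDI0457 doses, unless a result of any age is accepted. Every woman of childbearing potential who follows the schedule through Week 7 meets both gaps. The documents do not give the number of such women.

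The practical risk is small. Exclusion criterion 19 bars pregnant patients, Section 3.3.2 requires contraception from screening to 90 days after the last dose for those who are sexually active with a non-sterilized partner, and scheduled tests nominally bracket both doses. No endpoint, analysis set, sample size or error rate is affected. The point should be corrected because it concerns a safety rule and changes what sites do, but it does not threaten the trial.

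**What to change.** Add a mark to the Table 3 pregnancy-test row at Weeks 3 and 7, with the result read before the dose. This is preferable because it keeps the stricter safety rule. Hematology and chemistry are already drawn at both visits, so no visit or blood draw is added. The cost is up to two extra beta-HCG assays per woman of childbearing potential, and a late result could delay a vaccine dose within its ±3-day window.

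If 4-weekly testing was intended, amend Section 6.5.3 instead to say so and to state the maximum age of a result at dosing.

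Separately and optionally, Section 6.5.3 could state whether its biopsy requirement extends to the Week 10 biopsy, where Table 3 also has no test.
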